5.3.2. Immunogenicity Data

Any assays above LLOQ are considered accurate and their quantitated values will be reported. Values below the LLOQ or denoted as BLQ will be set to $0.5 \times \text{LLOQ}$ for analysis.

For calculating a fold rise, < LLOQ will be converted to $0.5 \times \text{LLOQ}$ for a numerator, and < LLOQ will be converted to LLOQ for a denominator when only one of either the numerator or denominator is < LLOQ. If both the numerator and denominator are < LLOQ, then both will be converted in the same way.

The LLOQs for each assay are listed in Table 10.

Table 10. LLOQ Titers for All Assay

Serotype	LLOQ
NT RSV A-50%	50
NT RSV B-50%	70
CCI	
	0.55
HAI: A CCI	10
HAI: A CCI	10
HAI: B	10
CCI	

Abbreviations: HAI = hemagglutination inhibition assay; CCI
 LLOQ = lower limit of quantification; NT = neutralizing titer; G; CCI

Values for sera that are insufficient (QNS), indeterminate results, or values recorded as “not done” will be set to “missing.” Additionally, any time point with no blood draws will not be included in the analysis. No imputation will be done for these missing values.

6. ANALYSES AND SUMMARIES

This section describes the analyses and summaries across all endpoints. In order to reconcile the protocol-specified endpoints (or estimands) and SAP template structure, the primary endpoints and secondary endpoints specified in the protocol are carried out in the “primary analysis” described in this section.

CCI

For each of the analysis sets (sentinel cohort, expanded cohort, combined sentinel and expanded cohorts), all safety and immunogenicity endpoints listed below will be summarized by age stratum, without combining the total age range. For the combined sentinel and expanded cohorts, the older age group will use a sentinel-cohort age range of 50 to 85 years.

6.1. Primary Endpoints

6.1.1. Local Reactions

6.1.1.1. Primary Analysis

Endpoint: Proportions of subjects reporting prompted local reaction within 14 days after vaccination.

- Analysis time points: Within 14 days after Vaccination 1.
- Analysis population: Safety population (sentinel cohort, expanded cohort, and combined sentinel and expanded cohorts).
- Analysis methodology: Descriptive summary statistics.
- Supporting objective: Primary objective.

Reporting Results:

Proportions of subjects reporting each and any local reactions after Vaccination 1 will be summarized by maximum severity level. Confirmed e-diary errors will be excluded from the analysis.

For each cohort, the percentage (%), the numerator (n) and denominator (N) used in the percentage calculation, and the corresponding 95% Clopper-Pearson CI will be presented for each vaccine group, by age stratum.

Figures: Bar charts with the proportions of subjects for each local reaction will be plotted for each vaccine group, by age stratum. The bar charts will be divided into severity subgroups to highlight the proportions of subjects by severity.

6.1.1.2. Additional Summary for Assessing Local Reactions After Vaccination 1

To support the assessment of local reactions, additional endpoints (as defined in Section 3.1.1) will be summarized. Confirmed e-diary errors will be excluded from these analyses.

Binary Endpoints

For each cohort, the percentage (%), the numerator (n) and denominator (N) used in the percentage calculation, and the corresponding 95% Clopper-Pearson CI will be presented for each vaccine group by age stratum for the following endpoints:

- Subjects reporting any severe local reaction on each day and any day (Day 1 through Day 14).

Continuous Endpoints

For each cohort, the following endpoints will be summarized by displaying n, mean, median, standard deviation, minimum, and maximum for each vaccine group, by age stratum:

- Duration of each systemic event after vaccination.
- Onset day of each systemic event after vaccination.
- Onset day of any systemic event after vaccination.

CCI

6.1.2. Systemic Events

6.1.2.1. Primary Analysis

Endpoint: Proportions of subjects reporting prompted systemic events (fever, fatigue, headache, vomiting, nausea, diarrhea, muscle pain, and joint pain) within 14 days after vaccination.

- Analysis time points: Within 14 days after Vaccination 1.
- Analysis population: Safety population (sentinel cohort, expanded cohort, and combined sentinel and expanded cohorts).
- Analysis methodology: Descriptive summary statistics.
- Supporting objective: Primary objective.

Reporting Results:

Proportions of subjects reporting each and any systemic events after Vaccination 1 will be summarized by maximum severity level. Confirmed e-diary errors will be excluded from the analysis.

For each cohort, the percentage (%), the numerator (n) and denominator (N) used in the percentage calculation, and the corresponding 95% Clopper-Pearson CI will be presented for each vaccine group, by age stratum.

Figures: Bar charts with the proportions of subjects for each systemic event will be plotted for each vaccine group, by age stratum. The bar charts will be divided into severity subgroups to highlight the proportions of subjects by severity.

6.1.2.2. Additional Summary for Assessing Systemic Events

To support the assessment of systemic events, additional endpoints (as defined in Section 3.1.2) will be summarized for each vaccine group, by age stratum. Confirmed e-diary errors will be excluded from these analyses.

Binary Endpoints

For each cohort, the percentage (%), the numerator (n) and denominator (N) used in the percentage calculation, and the corresponding 95% Clopper-Pearson CI will be presented for each vaccine group after Vaccination 1 for the following endpoints:

- Subjects reporting any severe systemic events on each day and any day (Day 1 through Day 14).

Continuous Endpoints

For each cohort, the following endpoints will be summarized by displaying n, mean, median, standard deviation, minimum, and maximum for each vaccine group, by age stratum:

- Duration of each systemic event after vaccination.
- Onset day of each systemic event after vaccination.
- Onset day of any systemic event after vaccination.

CCI

6.1.3. AEs

6.1.3.1. Primary Analysis

Endpoint: Proportions of subjects reporting AEs.

- Analysis time points: Within 1 month after Vaccination 1 and within 1 month after Vaccination 2 (expanded cohort only).
- Analysis population: Safety population (sentinel cohort, expanded cohort, and combined sentinel and expanded cohorts).
- Analysis methodology: Descriptive summary statistics.
- Supporting objective: Primary objective.

Reporting Results:

For each cohort, the percentage (%), the number of subjects, the denominator (N) used in the percentage calculation, and the corresponding 95% Clopper-Pearson CI for subjects reporting any AE, for each system organ class, and each preferred term within system organ class, will be presented for each vaccine group, by age stratum.

6.1.3.2 Additional Summary for Assessing Adverse Events

To support the assessment of AEs, additional endpoints by category (related AE, severe AE, SAE, MAE, immediate AE, AE leading to withdrawal), as defined in Section 3.1.4, will be summarized for all listed analysis time points among applicable cohort analysis populations, using similar analysis methodology and appropriate reporting results.

If any nonserious AEs are reported to occur before vaccination or more than 1 month after vaccination (outside of the protocol-specified reporting window), they will not be summarized, but will be included in the AE listings.

For AEs reported within 1 month after Vaccination 1 among the sentinel cohort, expanded cohort, and combined sentinel and expanded cohorts, each category will be compared between each RSV vaccine group and placebo, by age stratum. Between-group differences (RSV group – placebo group) in proportions and the associated 95% CIs will be provided using the Miettinen and Nurminen method.

Additionally, for the expanded cohort only, each category of AE reported within 1 month after Vaccination 1 will be compared between the coadministration (RSV and SIIV) and RSV groups within each dose/formulation, by age stratum. Between-group differences (RSV+SIIV group – SIIV group) in proportions and the associated 95% CIs will be provided using the Miettinen and Nurminen method.

Figures: Bar charts with the proportions of subjects for each category will be plotted for each vaccine group, by age stratum.

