3.1.4. Adverse Events

AE reporting will be based on the specific reporting period. Standard algorithms for handling missing AE dates and missing AE severity will be applied as described in the Pfizer Vaccine data standard rules.

As this is a Phase 1/2 study, with limited sample size included in each vaccine group, the value of applying the 3-tier approach is limited. Therefore, because of a small number of subjects in each dose/formulation group, safety assessment may be best carried out using descriptive statistics.

For AEs within 1 month after each vaccination, the interval calculation will be based on the study visit. Table 7 includes all AE intervals for each cohort. Any AEs with start date occurring within the lower bound and upper bound (inclusive) are included in the interval. It should be noted that Visit 2 and Visit 8 include intramuscular vaccination, thus AEs with start date at Visit 2 should be included in the next interval (AEs within 1 month after Vaccination 2). For consistency, this is applied to all intervals.

Table 7. AE Analysis Interval

Cohort	Interval	AE Start Date Lower Bound (Inclusive)	AE Start Date Upper Bound (Inclusive)
Sentinel cohort	AEs within 1 month after Vaccination 1	Visit 1	The day before Visit 3
Expanded cohort	AEs within 1 month after Vaccination 1	Visit 1	The day before Visit 2 ^a
Expanded cohort	AEs within 1 month after Vaccination 2	Visit 2	The day before Visit 3
CCI			

a. This visit includes a vaccination.

The following derivations/summaries will be included for each of the above:

1. Proportions of subjects reporting AEs during this interval summarized for each system organ class and preferred term (and “any event”), separately.
2. Proportion of subjects reporting any AE during this interval.
3. Proportion of subjects reporting any MAE during this interval.
4. Proportion of subjects reporting any SAE during this interval.
5. Proportion of subjects reporting any related AE during this interval.
6. Proportion of subjects reporting any severe AE during this interval.
7. Proportion of subjects reporting any intermediate AE. Intermediate AE is defined as an AE reported within the first 30 minutes after vaccination.
8. Proportion of subjects reporting any AE leading to withdrawal during this interval.

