4.2. Expanded Cohort

This cohort will include a total of 13 groups (12 vaccine groups and placebo), and 4 analysis populations will be defined.

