4.3. Combined Sentinel and Expanded Cohorts

This cohort will pool subjects from the sentinel cohort and expanded cohort. Only subjects who are randomized to receive SIIV at Visit 2 from the expanded cohort will be pooled with the sentinel cohort, across the dose/formulation groups. This cohort will include a total of 7 groups (6 vaccine groups and placebo), and 3 analysis populations will be defined.

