5.2.2.5. Assessing Interference

To understand whether concomitant administration of influenza and RSV vaccines in the expanded cohort interferes with the immune response to RSV vaccine, the GMR with associated 95% CI for RSV A- and RSV B-neutralizing antibody titers between sera drawn from subjects vaccinated with RSV vaccine with or without concomitant SIIV at 1 month after Vaccination 1 will be calculated.

Using RSV vaccine 60 µg as an example, the GMR will be calculated as follows:

- Numerator: RSV vaccine 60 µg/SIIV+placebo; and denominator: RSV vaccine 60 µg/placebo+SIIV.
- Numerator: RSV vaccine 60 µg+Al(OH)₃/SIIV+placebo; and denominator: RSV vaccine 60 µg+Al(OH)₃/placebo+SIIV.

To understand whether concomitant administration of influenza and RSV vaccines in the expanded cohort interferes with the immune response to SIV vaccine, the GMR with associated 95% CI for HAI for strains in SIV by comparing sera drawn from subjects vaccinated with SIV concomitantly with RSV vaccine at 1 month after Vaccination 1 or with SIV alone at 1 month after Vaccination 2 will be calculated.

- Numerator: RSV vaccine 60 µg/SIV+placebo; and denominator: placebo/placebo+SIV.
- Numerator: RSV vaccine 60 µg+Al(OH)₃/SIV+placebo, and denominator: placebo/placebo+SIV.
- Numerator: RSV vaccine 60 µg/SIV+placebo; and denominator: RSV vaccine 60 µg/placebo + SIV.
- Numerator: RSV vaccine 60 µg+Al(OH)₃/SIV+placebo; and denominator: RSV vaccine 60 µg+Al(OH)₃/placebo + SIV.

Similar combinations and comparisons will be done for the RSV vaccine 120-µg and 240-µg dose levels.

CCI

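### The coadministration AE difference in SAP 6.1.3.2 subtracts an SIIV group, but the stated comparator is the RSV group and no group has SIIV without RSV vaccine in that interval

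*SAP*

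**What the plan says.** Section 6.1.3.2 (Additional Summary for Assessing Adverse Events) has a paragraph for the expanded cohort only, on AEs within 1 month after Vaccination 1. It says that each AE category "will be compared between the coadministration (RSV and SIIV) and RSV groups within each dose/formulation, by age stratum". The following sentence gives the estimate: "Between-group differences (RSV+SIIV group – SIIV group) in proportions and the associated 95% CIs", by the Miettinen and Nurminen method.

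Other sections fix which arms exist and when SIIV is given:

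- Section 4.2: "This cohort will include a total of 13 groups (12 vaccine groups and placebo").
- Section 5.2.2.5 writes the control arm as placebo with placebo at the first vaccination and influenza vaccine at the second. It takes the influenza response to be compared "with SIV alone at 1 month after Vaccination 2 will be calculated" (SIV there stands for SIIV).
- Section 6.2.2.2 likewise describes a control group whose SIIV came after placebo.
- Section 3.1.4: "AEs with start date at Visit 2 should be included in the next interval (AEs within 1 month after Vaccination 2"). Table 7 accordingly ends the expanded cohort's Vaccination 1 interval on the day before Visit 2.

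**The concern.** Two adjacent sentences describe one contrast and disagree on the group to be subtracted: RSV in the first, SIIV in the second. These answer different questions. Subtracting the RSV group shows what adding SIIV does to the AE profile of a given RSV dose/formulation. Subtracting an SIIV group would show what adding RSV vaccine does to the AE profile of SIIV.

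The primary objective is to describe the safety of RSV vaccine alone or with SIIV. In the unredacted text this is the only between-group AE contrast that isolates the addition of SIIV. Section 2 says that programming rules and mock-up tables are prepared separately from the methods in this SAP, and the bracketed subtraction is what a programmer would code and print as a column label. Taken literally it has no arm to use in the interval. Forced, it would draw on the placebo control or on data from after Vaccination 2.

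**Working it through.** **Step 1. Reproduce the group count.** Section 2.2 gives 3 dose levels, each with or without Al(OH)₃. Section 3.2.2 gives two SIIV schedules: with RSV vaccine at Visit 1, or at Visit 2.

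3 doses × 2 formulations × 2 schedules + 1 placebo group = 13.

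This matches the 13 groups (12 vaccine groups and placebo) in sections 2.2 and 4.2. With equal allocation, 1014 / 13 = 78 per group and 78 / 2 = 39 per group and age stratum.

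**Step 2. List what each group has received between Visit 1 and the day before Visit 2.**

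| Groups | Number | Visit 1 | Visit 2 | SIIV without RSV vaccine in the interval? |
|---|---|---|---|---|
| Coadministration | 6 | RSV vaccine and SIIV | placebo | No |
| Sequential | 6 | RSV vaccine and placebo | SIIV | No |
| Control | 1 | placebo and placebo | SIIV | No |

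The arm sequences come from the numerators and denominators in section 5.2.2.5, which shows them for 60 µg and extends them to the other doses. The control row is confirmed by section 6.2.2.2. The interval comes from section 3.1.4 and Table 7. Groups matching an SIIV-only comparator: 0 of 13.

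**Step 3. Cross-check with section 4.3.** Of the pooled cohort it says: "Only subjects who are randomized to receive SIIV at Visit 2 from the expanded cohort will be pooled with the sentinel cohort", and then "This cohort will include a total of 7 groups (6 vaccine groups and placebo"). That agrees with 6 sequential groups and the control all having SIIV at Visit 2. It is not proof by itself, because the 7 groups describe the pooled cohort and the sentinel cohort alone already has 7 (section 4.1). The proof rests on steps 1 and 2.

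**Step 4. Try each possible meaning of the SIIV group.**

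- *Sequential RSV arm:* this is the intended comparator, but it has had no SIIV in the interval, so the label is wrong.
- *Placebo control in the same interval:* it too has had no SIIV. The contrast would repeat the RSV-minus-placebo comparison in the preceding paragraph of 6.1.3.2, and the control has no dose/formulation to match on.
- *Placebo control after Vaccination 2:* this is SIIV alone, but in a different interval from the one the paragraph states.

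**Step 5. Compare with the parallel immunogenicity contrast.** Section 5.2.2.5 assesses the RSV response "between sera drawn from subjects vaccinated with RSV vaccine with or without concomitant SIIV at 1 month after Vaccination 1 will be calculated". Section 6.2.1.2 also compares each coadministration group with the RSV-only (SIIV later) group of the same dose/formulation. Both agree with the sentence in words in 6.1.3.2, not with its formula.

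**Step 6. Size.** 6 dose/formulations × 2 age strata = 12 group pairs, each 39 versus 39 as randomized. Section 6.1.3.2 lists six categories (related, severe, serious, medically attended, immediate, leading to withdrawal), so 12 × 6 = 72 differences at most. This counts planned contrasts, not errors.

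**The case against.** The strongest defence is that a careful reader would not go wrong. The preceding sentence fixes the cohort, the interval and the matching on dose/formulation. Matching excludes the placebo control, and the interval excludes data from after Vaccination 2. The SAP elsewhere identifies the sequential arm by its later SIIV, so the term may be loose shorthand for the right arm, or a mistyped word. The rule also sits in an additional summary. The primary AE analysis in 6.1.3.1 reports percentages by group with Clopper-Pearson intervals and does not use this contrast. Sections 5.1.1 and 5.1.2 exclude hypothesis tests and decision rules.

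All of that stands as a limit on the consequence. It does not make the formula correct: as shorthand, the term names the sequential arm by a vaccine it has not yet received, and the paragraph contrasts that arm with one that has.

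One passage could be read the other way. Section 4.2.2, defining the evaluable influenza population, mentions placebo given with SIIV at Visit 1, which might suggest a further arm. The count of 13 leaves no room for one, and sections 5.2.2.5 and 6.2.2.2 both place the control group's SIIV after placebo.

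**Conclusion.** The formula is wrong as written. It contradicts the sentence before it and names a comparator that none of the 13 groups supplies in the stated interval. The effect is minor. It concerns up to 72 descriptive differences in a supporting summary, the intended arm can be recovered from the text, and no bias follows if that arm is used. It is most likely a drafting slip. The conclusion assumes that the arm sequences shown for 60 µg in section 5.2.2.5 apply to the other two doses, as that section says of its comparisons, and that the 13 groups are the full design.

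**What to change.** In section 6.1.3.2, change the subtracted term from the SIIV group to the RSV group of the same dose/formulation, and define it there as the group receiving RSV vaccine and placebo at Visit 1 and SIIV at Visit 2. Use the same label in the table mock-ups and programming rules. The contrast then agrees with the preceding sentence and with sections 5.2.2.5 and 6.2.1.2, and gives 6 estimable differences per age stratum for each AE category. The cost is one term in one sentence, with no new data, no change of method and no change of design.

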6.1.4. SAEs

6.1.4.1. Primary Analysis

Endpoint: Proportions of subjects reporting SAEs.

- Analysis time points: Through 12 months after Vaccination 1.
- Analysis population: Safety population (sentinel cohort, expanded cohort, and combined sentinel and expanded cohorts).
- Analysis methodology: Descriptive summary statistics.
- Supporting objective: Primary safety objective.

Reporting Results:

The percentage (%), the number of subjects (n), the denominator (N) used in the percentage calculation, and the corresponding 95% Clopper-Pearson CI for subjects reporting any SAEs, for each system organ class, and for each preferred term within system organ class, will be presented for each vaccine group, by age stratum.

Figures: None.

CCI
[Redacted]

6.1.5. MAEs

MAEs will be analyzed in a similar way as SAEs (Section 6.1.4).

6.2. Secondary Endpoint(s)

The evaluable immunogenicity population definition included a required window of 1 month after the vaccination (either RSV or SIV). However, almost all RSV immunogenicity endpoints are evaluated at multiple time points. To ensure a true description of immune response kinetics, the following rules are used for the time points included in the analyses:

1. 1 Month after Vaccination 1 – 27 to 42 days after Vaccination 1 (per the evaluable immunogenicity definition, with an additional relaxation of -1 to +7 days compared with the protocol-required window)
2. 2 Weeks after Vaccination 1 – 11 to 21 days after Vaccination 1 (relaxation of ± 3 days)

3. 2 Months after Vaccination 1 – 49 to 77 days after Vaccination 1 (relaxation of ± 1 week)
4. 3 Months after Vaccination 1 – 77 to 112 days after Vaccination 1 (relaxation of -1 to +1 week)
5. 6 Months after Vaccination 1 – 154 to 224 days after Vaccination 1 (relaxation of -2 to +2 weeks)
6. 12 Months after Vaccination 1 – 336 to 392 days after Vaccination 1 (relaxation of -2 to +2 weeks)

CCI

6.2.1. RSV A– and RSV B–Neutralizing Antibody Titers

6.2.1.1. Primary Analysis

Endpoint: RSV A– and RSV B–neutralizing antibody titers.

- Analysis time points: From before to up to 6 months after Vaccination 1.
- Analysis populations: Evaluable RSV immunogenicity population (sentinel cohort, expanded cohort, and combined sentinel and expanded cohorts).
- Analysis methodology: Descriptive summary statistics.
- Supporting objective: Secondary objective.

Reporting Results:

GMTs at the above-mentioned time point and associated 95% CIs will be summarized by vaccine group for both RSV A– and RSV B–neutralizing antibody titers. Also, GMFRs from before Vaccination 1 to each above-mentioned time point and associated 95% CIs will be summarized by vaccine group for both RSV A– and RSV B–neutralizing antibody titers.

Figures:

RCDCs for RSV A– and RSV B–neutralizing antibody titers for the 2 time points (before Vaccination 1 and 1 month after Vaccination 1), by vaccine group, will be generated for each age stratum among the combined sentinel and expanded cohorts.

6.2.1.2. Additional Summary

For the sentinel cohort, expanded cohort, and combined sentinel and expanded cohorts, GMTs at all other applicable visits after Vaccination 1 will be summarized along with associated 95% CIs for each vaccine group, by age stratum, for both RSV A– and RSV B–

neutralizing antibody titers. Additionally, all fold rises specified in Section 3.2.1 will be summarized with GMFRs and associated 95% CIs.

The following comparisons will be made in order to assess the interference of SIIV coadministration with the immune response induced by RSVpreF among the expanded cohort:

- GMTs for RSV A NT and RSV B NT will be compared between the RSVpreF with SIIV group and the RSVpreF-only (or SIIV after RSVpreF) group for each dose/formulation, by age stratum. GMRs and associated 95% CIs will be calculated from 1 month through 12 months after Vaccination 1.

Figures:

For the combined sentinel and expanded cohorts, NT GMT kinetics for each vaccine group will be plotted across all visits, by age stratum.

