2.2. Study Design

This is a Phase 1/2, randomized, placebo-controlled, observer-blind, dose-finding first-in-human (FIH) study.

The study will evaluate the safety, tolerability, and immunogenicity of up to 6 RSV vaccine candidates with CCI [REDACTED] at 3 escalating dose levels of 60 µg CC [REDACTED] 120 µg CC [REDACTED] and 240 µg CCI [REDACTED] of the prefusion RSV F antigen, with or without aluminum hydroxide (Al[OH]₃), when administered alone or concomitantly with SIIV.

This study will utilize a sentinel cohort (Phase 1) and an expanded cohort (Phase 2) for each dose level in each age group. The age groups will run in parallel but independently from each other.

In the sentinel cohort (Phase 1), subjects will be enrolled into 2 age groups with equal numbers of subjects:

- Male and female subjects 18 to 49 years of age.
- Male and female subjects 50 to 85 years of age.

In the expanded cohort (Phase 2), subjects will be enrolled into 2 age groups with equal numbers of subjects:

- Male and female subjects 18 to 49 years of age.
- Male and female subjects 65 to 85 years of age.

In the sentinel cohort, approximate 168 subjects will receive a single intramuscular dose of the RSV vaccine candidate with or without Al(OH)₃ or placebo at Vaccination 1. Central randomization will take place in a 3:3:1 ratio for each dose level, by age stratum.

In the expanded cohort, 1014 subjects will be randomized equally across all dose/formulation levels, with or without SIIV, by age group via center-based randomization. This will include a total of 13 groups with an equal randomization ratio. Subjects in this cohort will receive 2 intramuscular injections at Visit 1 (Vaccination 1) and 1 intramuscular injection at Visit 2 (Vaccination 2). CCI [REDACTED]

CCI
[Redacted]

For both sentinel-cohort and expanded-cohort subjects, key safety data include electronic diary (e-diary) reports of local reactions and systemic events that occur within 14 days after Vaccination 1 (RSV vaccine or placebo). Adverse events (AEs) are collected from informed consent until 1 month after Vaccination 1 (Visit 3 for the sentinel cohort); and from consent until 1 month after Vaccination 2 (Visit 3 for the expanded cohort). AEs occurring up to 48 hours after blood draws are also collected. Medically attended AEs (MAEs) are collected after the AE collection period. Serious adverse events (SAEs) are being collected for all subjects from informed consent through 12 months after Vaccination 1.

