CCI
[Redacted]

Blood samples are collected from all subjects for antibody testing. For sentinel-cohort subjects, blood samples are collected before Vaccination 1 and 2 weeks and 1, 2, 3, 6, and 12 months after Vaccination 1. For expanded-cohort subjects, blood samples for antibody testing are collected before Vaccination 1 and 1, 2, 3, 6, and 12 months after Vaccination 1.

CCI
[Redacted]

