4.1. Sentinel Cohort

This cohort will include a total of 7 groups (6 vaccine groups and placebo), and 3 analysis populations will be defined. The placebo group will pool all subjects who were randomized or received placebo within each dose cohort.

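### The combined-cohort RSV neutralizing-titer kinetics figure changes its sample at week 2, from about 51 subjects per group to about 12 sentinel subjects and back

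*SAP*

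**What the plan says.** The figure is specified in SAP section 6.2.1.2 for the combined sentinel and expanded cohorts: "NT GMT kinetics for each vaccine group will be plotted across all visits, by age stratum". Section 4.3 forms that combined cohort from all sentinel subjects plus the expanded-cohort subjects randomized to receive SIIV at Visit 2, giving seven groups.

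The sampling schedules in section 2.2 differ. Sentinel subjects are bled before vaccination, at 2 weeks, and at 1, 2, 3, 6 and 12 months. For the other cohort: "For expanded-cohort subjects, blood samples for antibody testing are collected before Vaccination 1 and 1, 2, 3, 6, and 12 months after Vaccination 1". There is no 2-week draw.

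Section 5.2.2.1 computes each GMT as a plain log-scale mean of whatever is available at that time point. Section 6 sets the older stratum of the combined cohort at 50 to 85 years, although section 2.2 enrols older expanded-cohort subjects only from 65 to 85.

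**The concern.** Week 2 is the only visit between baseline and month 1, so both parts of the figure that could show how fast titers rise, and whether they have begun to fall by 1 month, depend on it. If about three quarters of the contributing subjects are absent at that one visit and present on either side, a level difference between cohorts appears as a change over time. A reader comparing early kinetics across doses and formulations could take it for part of the vaccine response. The unredacted SAP text neither restricts nor marks the 2-week point, does not require a common set of subjects, and does not ask for n per visit on the figure.

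**Working it through.** **Cell sizes, from the SAP's own totals**

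Inputs for the sentinel cohort (sections 2.2 and 4.1):
- Total: "In the sentinel cohort, approximate 168 subjects will receive a single intramuscular dose of the RSV vaccine candidate with or without Al(OH)₃ or placebo".
- Age: "In the sentinel cohort (Phase 1), subjects will be enrolled into 2 age groups with equal numbers of subjects".
- Allocation: "Central randomization will take place in a 3:3:1 ratio for each dose level, by age stratum", with three dose levels.
- Placebo: "The placebo group will pool all subjects who were randomized or received placebo within each dose cohort".

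Calculation:
- 168 / 2 age groups / 3 dose levels = 28, which splits 3:3:1 into 12, 12 and 4.
- Pooled placebo per age stratum: 3 × 4 = 12.
- Check: 2 × (6 × 12 + 12) = 168, the stated total.

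Inputs for the expanded cohort (section 2.2): 1014 subjects, 13 equal groups, and "In the expanded cohort (Phase 2), subjects will be enrolled into 2 age groups with equal numbers of subjects".
- 1014 / 13 / 2 = 39 per group and age stratum.
- Check: 13 × 2 × 39 = 1014, the stated total.

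Each combined group takes one sentinel group and one expanded group: 12 + 39 = 51 per age stratum.

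| Visit | Contributing subjects per group and age stratum |
|---|---|
| Baseline | 12 + 39 = 51 |
| 2 weeks | 12 |
| 1, 2, 3, 6, 12 months | 12 + 39 = 51 |

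So 39 / 51 = 76% of the sample is missing at week 2 by design. These are randomized counts. With 10% non-evaluable (assumed) they become about 11 and 46.

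**Displacement if the cohorts differ in level**

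Let r be the ratio of sentinel to expanded GMT. The log of the combined GMT is (12 × sentinel + 39 × expanded) / 51. The sentinel-only point therefore differs from the combined value by a factor r^(39/51).

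| Assumed r | Displacement of the 2-week point | Apparent fall from week 2 to month 1 with no true change |
|---|---|---|
| 1.2 | 1.15 | 1 − 1/1.15 = 13% |
| 1.5 | 1.36 | 1 − 1/1.36 = 27% |

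The inverse ratios displace the point downward by the same factors and give an apparent rise. The SAP contains no value for r.

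**Displacement by chance alone**

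If both cohorts come from one population and each subject's deviation on the log scale is the same at both visits, the SD of the step is SD × √(1/12 − 1/51) = 0.252 × SD.
- ln-titer SD 0.8 (assumed): exp(0.202) = 1.22-fold.
- SD 1.0: exp(0.252) = 1.29-fold.
- SD 1.2: exp(0.303) = 1.35-fold.

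Full persistence is the upper case. With between-visit correlation ρ, the variance of the step from week 2 (12 subjects) to month 1 (51 subjects) is SD² × (1/12 + 1/51 − 2ρ/51). Following the same 12 subjects gives SD² × 2(1 − ρ)/12. The excess is SD² × (1/12 − 1/51) × (2ρ − 1). It is complete at ρ = 1 and vanishes at ρ = 0.5.

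**Older stratum**

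Subjects aged 50 to 64 can come only from the sentinel cohort. Their share at week 2 is 51/12 = 4.25 times their share at every other visit. If half of the older sentinel subjects were in that range (assumed), they would be 50% of the 2-week point and 0.5 × 12/51 = 12% of the others. In the 18-to-49 stratum both cohorts have the same age range, so the documents give no age-based reason for a difference.

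**The case against.** The strongest reply is that the same-subject information is already planned. Sections 6.2.1.1 and 6.2.1.2 tabulate GMTs and GMFRs for the sentinel cohort on its own. Section 5.2.2.2 limits fold rises to subjects with values at both visits, so the sentinel 2-week GMFR is free of any composition effect. This stands and confines the point to the figure, but a table does not correct a figure that is read by itself.

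Second, the SAP does not say that the points are joined, and section 2 leaves mock-up figures to separate documents. That also stands: connecting lines are an inference from a kinetics plot. The mock-ups are nevertheless to follow the SAP, whose instruction covers all visits. Redacted text next to this section could also contain another figure.

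Third, with 12 subjects and an ln-titer SD of 0.8 to 1.2, the 95% CI of the 2-week GMT is about 1.66- to 2.14-fold either way, wider than the 1-SD chance step. True, but the figure is not required to show intervals, and a wide interval does not tell the reader that the population has changed.

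Three stronger readings are tempting and not supported:
- A reader might infer that the early part of the curve is merely an artefact. It is not: it contains the real vaccine response plus an error of unknown size and sign.
- A reader might take the phrase "To ensure a true description of immune response kinetics" in section 6.2 as a promise that this figure breaks. That sentence introduces day windows for sampling and says nothing about who contributes to a pooled plot.
- A reader might infer that dose selection is compromised. Section 5.1 sets no tests or decision rules, and the dose-related interim analyses in section 7 are triggered by 1-month results. At week 2 every group is sentinel-only, so doses are compared like with like at that visit.

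**Conclusion.** The point holds as a cheap improvement of low severity. The change from about 51 to about 12 subjects and back follows exactly from the SAP's totals, ratios and sampling schedules. Apparent changes into and out of week 2 on the combined figure therefore partly reflect a change of sample, systematically in the older stratum and by chance in the younger.

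How large the effect will be cannot be known from the SAP. The 1.15- to 1.36-fold displacement rests on an assumed cohort ratio of 1.2 to 1.5, with the inverse equally possible. The 1.22- to 1.35-fold chance step rests on an assumed ln-titer SD of 0.8 to 1.2 and on full persistence of subject deviations, and is smaller otherwise. No tabulated result and no formal inference is affected.

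**What to change.** Change the figure specification in SAP section 6.2.1.2 in one of two ways:

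1. Omit the 2-week visit from the combined-cohort curve, which then runs from baseline to 1 month and onward on about 51 subjects per group, and add a sentinel-only kinetics plot that includes week 2 on the same 12 or so subjects throughout.
2. Keep the 2-week value on the combined figure as an unconnected point labelled as sentinel cohort only, beside the baseline and 1-month GMTs of those same subjects.

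In either case, print n at each visit under the figure. Apart from missing samples, both options remove the composition effect from the plotted curve. No new data or analysis is needed. The cost is one extra figure under the first option, and under either option the combined curve itself has no early time point.
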